3. INVESTIGATIONAL PLAN

3.1. Study Design

This will be a randomized, double-blind, single-center, vehicle-controlled, within-subject comparison study of the study products, CCP-020 (Diacerein 1%) topical ointment, vehicle ointment, and an untreated irradiated non-occluded (open) control site. A total of 4 application sites (2 cm x 2 cm each) will be marked on the subject's back and distributed so that 2 sites are on each side of the back. One side of the back will be designated for irradiation after approximately 24 hours (± 4 hours) of study product application and the other side will remain non-irradiated. An additional site will be marked on the "irradiated side" of the back. The site will receive no study product, but will be irradiated at Challenge to serve as an untreated irradiated non-occluded control.

A defined area (approximately 50 cm²) on the infrascapular region of each subject's back will be irradiated to determine the minimal erythema dose (MED) of ultraviolet (UV) light.

During the 3-week Induction Phase, 0.2 mL of each study product will be applied to 2 sites twice each week (Monday and Thursday) for approximately 24 hours (± 4 hours) under occlusive patch conditions (6 applications). After patch removal, all application sites will be evaluated and one application site of each study product will be irradiated with 2 times the subject's MED using the full Xenon lamp spectrum. The sites will be evaluated by a trained evaluator. All sites will be reevaluated post irradiation, at approximately 48 hours later when irradiated on Tuesdays and at approximately 72 hours later when irradiated on Fridays except when irradiated on the last Friday of the Induction Phase or if a subject is taking a missed visit during induction, the sites will not be evaluated. These procedures will be performed each week for 3 weeks of the Induction Phase. Dermal reactions at the application sites will be evaluated using a visual scale that rates the degree of erythema, edema, and other signs of cutaneous irritation (see [Table 3](#) and [Table 4](#)).

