At the end of the Induction Phase, the subjects will enter a Rest Period of 10-17 days and then a Challenge Phase. One application/irradiation session may be missed during the Induction Phase. It must be made-up during Week 4. An additional application of study product may be applied on the Monday of rest week 4 if the subject had missed an irradiation session during the induction phase of the study. In either case, no evaluation will be required following irradiation.

At Challenge, each study product will be applied in an amount of 0.2 mL to 2 naive sites once for approximately 24 hours (± 4 hours) under occlusive patches. After 24 hours (± 4 hour) of product application, all sites will be evaluated and one application site of each product and the additional untreated control site will be irradiated. The sites will be examined for dermal reactions at approximately 24 hours (± 4 hours), 48 hours (± 4 hours), and 72 hours (± 4 hours) post-irradiation. A Rechallenge will be performed if a cutaneous response observed during the Challenge Phase indicates possible photosensitization or at the discretion of the Investigator.

The safety endpoints for this study are irritation responses during the Induction Phase, positive responses at Challenge (i.e., reactions indicative of a sensitization response) and adverse events.

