3.3.3. Interruption or Discontinuation of Treatment

A reaction of at least moderate erythema (2) accompanied with mild, but definite edema (1) to a study product observed after the first patch application/irradiation sequences of the Induction Phase may indicate the subject to be pre-sensitized, and may cause the discontinuation of the subject from the study.

After the second reading of the Induction Phase, either of the following conditions will require the study product be applied to a naive patch site under semi-occlusive patch conditions:

- Reaction of >50% “p” or “p” with no erythema, minimal/doubtful erythema, or definite erythema; or “D” (see [Tables 3 and 4](#));
- Any reaction of definite erythema with definite edema.

Study product may not be relocated more than twice.

The 3 weeks of continuous patch contact during the Induction Phase frequently results in tape-related irritation that is exacerbated by warm weather, but which occurs among some individuals irrespective of the season. Tape-related irritation will not be graded as a photosensitivity response at the patch site, but will be noted separately on the CRF. Severe tape-related irritation will necessitate a change in the application site. As above, the application site will only be changed twice and then the subject must be discontinued.

One application/irradiation session may be missed during the Induction Phase. It must be made-up during Week 4. In this case, no evaluation will be required following irradiation. Only one missed patch application for study product is allowed. A subject must be discontinued and considered not complete if more than one application is missed.

In accordance with legal requirements and ICH-GCP guidelines, every subject or his/her legal representative has the right to refuse further participation in the study at any time and without providing reasons (see also [Section 5.3](#)). A subject's participation is to be terminated immediately upon his/her request. The Investigator should seek to obtain the reason and record this on the case report form (CRF).

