3.5.2. Visit Schedule

A summary of the visit schedule and assessments is presented in [Table 2](#).

Table 2: Visit Schedule and Assessments

	Screening	Day 1 ^a (M)	Induction				Rest	Challenge (Week 6)				
			M 8, 15	Tu 2, 9, 16	Th 4, 11, 18	F 5. 12, 19		Week 4 & 5	M	Tu	W	Th
Informed consent	X											
Inclusion/Exclusion	X	X										
Medical history	X											
Demographic information	X											
Fitzpatrick Skin Typing	X											
UPT		X										X
MED irradiation/evaluation		X ^b										
Randomization		X										
Product application		X	X		X			X				
Application site evaluations			X ^c	X	X	X ^d			X	X	X	X
Application site irradiation				X		X ^d		X	X			
Make-up evaluation/application							X ^e					
Make-up evaluation/irradiation							X ^e					
Review of concomitant medications	X	X	X	X	X	X	X ^f	X	X	X	X	X
Review of AEs	X	X	X	X	X	X	X ^f	X	X	X	X	X

a Screening and the first day of Induction (Day 1) may take place on the same day.

b MED irradiation on Day 1 and MED evaluation on Day 2.

c The first Monday (Week 1) of the Induction Phase.

d Evaluations will not be conducted after irradiation on the last Friday of the Induction Phase. Untreated control site will also be irradiated.

e Make-up evaluation/application and evaluation/irradiation are performed as necessary (see [Section 3.5.1](#)).

f Concomitant medications and AEs will be reviewed only for subjects who are required to return to the test facility for make-up visits during Rest Period - Week 4.

Note: The visit schedule may be revised if necessary.

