4.3. Subject Populations for Analysis

All subjects who receive treatment will be evaluable for AEs. The evaluation of photosensitization will be based on all subjects who complete the Challenge Phase of the study. Subjects who completed Challenge are those who have received at least 6 applications/irradiation of study products, and at least 11 subsequent evaluations during Induction, completed the Rest Phase and have received one application of study products at Challenge, subsequent irradiation and at least 4 evaluations (3 post-irradiation evaluations) for that product. The analysis of local tolerability (photo irritation) will be based off all subjects who complete the Induction Phase of the study. Subjects who completed Induction are those who have received at least 6 applications/irradiation of study products, and at least 11 subsequent evaluations during Induction.

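### The Induction tolerability analysis is limited to Induction completers, so a skin reaction that stops a subject early removes that subject's scores from it

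*Combined protocol and SAP*

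**What the plan says.** Section 3.1 makes Induction irritation an endpoint: "The safety endpoints for this study are irritation responses during the Induction Phase, positive responses at Challenge", with adverse events as the third.

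Section 4.3 sets a population for each:

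- Adverse events: "All subjects who receive treatment will be evaluable for AEs".
- Photosensitization: subjects who complete Challenge.
- Tolerability: "The analysis of local tolerability (photo irritation) will be based off all subjects who complete the Induction Phase of the study". Completing Induction means "at least 6 applications/irradiation of study products, and at least 11 subsequent evaluations during Induction".

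Sections 4.1 and 4.6.1 describe an ANOVA, with factors subject and treatment, on each subject's mean Induction score at each site. All pairwise comparisons follow. Section 4.6.1 also plans frequency counts of every assigned score by time point and treatment, and the incidence of reactions. It names no population for any of these. The ANOVA is the only inferential analysis of Induction scores, so the natural reading is that the tolerability population of Section 4.3 governs it.

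Section 3.3.3 deals with early reactions. "A reaction of at least moderate erythema (2) accompanied with mild, but definite edema (1) to a study product", seen after the first sequences, "may indicate the subject to be pre-sensitized, and may cause the discontinuation of the subject from the study". After the second reading, definite erythema with definite edema (and certain other reactions) leads to relocation to a naive site, at most twice. One missed session may be made up in Week 4.

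Sections 3.6.1, 3.6.2.1 and 3.6.6 each say that a response gradable on Table 3 or Table 4 is not an adverse event.

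**The concern.** Membership of the tolerability set can depend on the outcome the set is used to measure. A strong early reaction can lead to discontinuation, discontinuation makes the completer threshold unreachable, and the score then leaves the analysis of irritation.

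Full Induction exposure is a sensible condition for interpreting Challenge. It is not needed to observe irritation, because one application and one reading already give a score. The documents give no reason for applying the completer rule to tolerability.

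The study has no efficacy endpoint; its purpose is to describe skin safety. At stake is whether a score bad enough to stop a subject is certain to appear in any planned summary.

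**Working it through.** **1. The plan's own threshold.** Section 3.1 gives two applications a week for 3 weeks, "under occlusive patch conditions (6 applications"): 2 × 3 = 6. Readings from Table 2 (Section 3.5.2):

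- at patch removal: Days 2, 5, 9, 12, 16, 19 = 6
- after irradiation: Days 4, 8, 11, 15, 18 = 5, because "Evaluations will not be conducted after irradiation on the last Friday of the Induction Phase"

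Total 6 + 5 = 11. The threshold of 6 and 11 is therefore the whole schedule. The Week 4 make-up gives room for a missed session, but not for a subject who has been stopped.

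**2. Who fails it.** Counts for a subject stopped at a given reading, before any application due that day:

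| Stopped at | Applications | Evaluations | Completer? |
|---|---|---|---|
| Day 2 | 1 | 1 | no |
| Day 4 | 1 | 2 | no |
| Day 8 | 2 | 4 | no |
| Day 12 | 4 | 7 | no |
| Day 18 | 5 | 10 | no |
| Day 19 | 6 | 11 | yes |

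Any stop before the Day 19 reading excludes the subject. The stop named in Section 3.3.3, after the first sequence, falls in the first two rows.

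**3. Where else the score could appear.**

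- Adverse event tables: no, because Table 3/4 responses are not adverse events.
- CRF reason for withdrawal (Section 3.3.3): recorded, but no table is planned.
- Compliance summary (Section 4.3.2): all randomized subjects, but no skin score.
- Frequency and incidence tables (Section 4.6.1): undetermined, because no population is named.

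**4. Size.** The documents give no rate of reaction-driven stops, so what follows is illustration under assumed counts. Take 50 completers, of whom c have a reactive site, k subjects stopped for a reaction, and d other dropouts without one. Completers show c/50. All treated show (c + k)/(50 + k + d). Completers understate only if k/(k + d) > c/50.

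| c, k, d | Completers (exact 95% CI) | All treated (exact 95% CI) |
|---|---|---|
| 0, 3, 0 | 0/50 = 0% (0 to 7.1%) | 3/53 = 5.7% (1.2 to 15.7%) |
| 2, 3, 5 | 2/50 = 4.0% (0.5 to 13.7%) | 5/58 = 8.6% (2.9 to 19.0%) |
| 5, 1, 10 | 5/50 = 10.0% (3.3 to 21.8%) | 6/61 = 9.8% (3.7 to 20.2%) |

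In the last row 1/11 = 0.091 is below 0.10, so there is no understatement. These differences arise only if the incidence tables use the completer set. The plan itself specifies confidence intervals only for photosensitization.

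*Mean score at one site.* Assume 3 subjects stopped at Day 4 with the trigger score at one or both of their 2 readings, all other scores 0, and erythema and edema summed (2 + 1 = 3; the summing is an assumption). Each stopped subject's mean is 1.5 to 3. The site mean moves from 0 to between 3 × 1.5/53 = 0.085 and 3 × 3/53 = 0.170. For erythema alone it moves to between 3 × 1/53 = 0.057 and 3 × 2/53 = 0.113.

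*Planned contrasts.* With all four sites read in each subject, a pairwise contrast is the average within-subject difference. If the 3 subjects react only at the irradiated site, the irradiated-minus-non-irradiated contrast moves by the same 0.085 to 0.170. If they react equally at both sites, their differences are 0 and a completer contrast D becomes 50D/53 = 0.943D, slightly smaller. The effect on the contrasts therefore depends on which sites react, and cannot be derived.

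**The case against.** The strongest case against has four parts.

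- *The early reaction may not be irritation.* Section 3.3.3 says it may indicate pre-sensitization, and an existing allergy arguably does not belong in an irritation mean. This stands as a question of interpretation. The text says only that it may be so, and that is no reason for the score to go unreported.
- *The route is narrow.* The stop is discretionary, and reactions after the second reading lead to relocation. A relocated subject who finishes stays in the set with all scores. This stands and limits how often the problem can occur. A later reaction-driven stop would rest on the unclear plural in the first-sequence rule or on the investigator's general discretion.
- *Section 4.6.1 tabulates all assigned scores.* A reader might infer that a stopped subject's reaction is lost from every analysis. The documents do not support that, because those tables name no population and, read literally, could include it. Exclusion is established for the tolerability analysis of Section 4.3 and only possible for the tables.
- *The SAP is still to be finalised (Section 3.4.5.2).* True, but Section 4.3 already states a rule. If the sponsor intended all treated subjects, that rule says otherwise and still needs changing.

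A reader might also infer that the photosensitization conclusion is biased. That is not supported: the diagnosis rests on Challenge readings, and a subject stopped early in Induction has none to lose.

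**Conclusion.** The point holds in limited form. Section 4.3 restricts the tolerability analysis, and on the natural reading the Induction ANOVA, to subjects with the full schedule. A subject stopped for a reaction before the Day 19 reading is excluded because of the response being measured, and the adverse event analysis does not recover the score.

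The likely direction is understatement of irritation. That assumes reactors are a larger share of non-completers than of completers. Neither the size nor the effect on the planned site contrasts can be derived from the documents. It should be corrected because it touches a named safety endpoint and the correction uses data already collected.

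**What to change.** In Sections 4.3 and 4.6.1, or in the SAP:

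1. Base the Induction tolerability analysis, and the Induction frequency and incidence tables, on all subjects with at least one application and one post-application score. Show the number read at each time point.
2. Keep the same ANOVA on the per-subject, per-site mean already specified, with the Section 4.3 completer set as a supportive analysis.
3. Tabulate discontinuations for skin reactions, with their scores, by product and irradiation status.

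The cost is wording and one added table, with no new visits, subjects or data. The downside is that a stopped subject's mean rests on fewer readings (2 rather than 11 for a stop at Day 4) and on less cumulative exposure. Irritation figures may also look less favourable.

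Separately, two contradictions must be reconciled; no position is taken on which text should stand. Section 3.5.1 gives 4 Induction applications where Section 3.1 gives 6, and the completer threshold depends on that count. On severe tape irritation, Section 3.3.3 changes the site at most twice and then discontinues the subject, whereas Section 3.6.6 stops the affected site and keeps the subject in the study.

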4.3.1. Background and Demographic Characteristics

Descriptive statistics will be used to summarize demographic characteristics (age, gender, Fitzpatrick skin type, and race) and background characteristics for the randomized subject population. Past/coexistent medical history information for all randomized subjects will be presented in a by-subject listing.

4.3.2. Study Product/Visit Compliance

Descriptive statistics will be used to summarize study product compliance for the randomized subject population.

4.4. Prior and Concomitant Medications

Prior and concomitant medication information for all randomized subjects will be presented in a by-subject listing.

4.5. Efficacy Evaluation

This section is not applicable to this study.

4.6. Safety Evaluation

4.6.1. Assessment of Responses

All assigned scores during Induction and Challenge will be summarized by frequency counts by time point and treatment. The incidence of reactions will be summarized by frequency counts for each treatment. The mean score by subject and treatment, including all scores assigned during Induction, will be analyzed using Fisher's least significant differences in the analysis of variance (ANOVA) with factors subject and treatment. All pairwise comparisons will be performed: CCP-020 (Diacerein 1%) topical ointment on both the irradiated and non-irradiated sides, and vehicle ointment on both the irradiated and non-irradiated sides.

4.6.2. Photosensitivity

The determination of dermal photosensitization potential will be made by the Investigator based on specific scoring criteria derived from observations in the Challenge Phase of the study and confirmed in the Rechallenge Phase, if necessary. The incidence of photosensitization reactions will be summarized by frequency counts for each treatment. If photosensitization occurs, the 95% confidence interval for the proportion of subjects with photosensitization for each product will be calculated. Photosensitivity will not be determined by statistical methods.

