2. STUDY OBJECTIVES

The objective of this study is to determine the photoallergic potential of CCP-020 (Diacerein 1%) topical ointment when topical application to skin is followed by light exposure.

In addition, safety will be assessed by evaluation of any adverse events (AEs) reported during the study.

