3.3. Study Population

3.3.1. Subject Population

A sufficient number of subjects will be enrolled in order to provide 50 completed subjects evaluable for analysis; an individual subject will be allowed to participate in the study one time only.

A rationale for the choice of sample size is provided in [Section 4.2](#) of this protocol.

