4.2. Sample Size and Power Considerations

The sample size of 50 evaluable subjects conforms to industry and regulatory standards for determination of irritation/sensitization when topical application to skin is followed by light exposure.

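### The 95% confidence interval for photosensitization is planned only if a reaction occurs, so a zero count gets no upper bound, although 0/50 is compatible with a rate up to about 7.1%

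*Combined protocol and SAP*

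**What the plan says.** Section 2 sets the aim: "The objective of this study is to determine the photoallergic potential of CCP-020". The outcome that answers it is the proportion of subjects diagnosed as photosensitized. Section 4.3 fixes the denominator: "The evaluation of photosensitization will be based on all subjects who complete the Challenge Phase of the study". Section 3.3.1 plans enrolment to yield "50 completed subjects evaluable for analysis".

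Section 4.6.2 plans two outputs for this outcome. The first is unconditional: "The incidence of photosensitization reactions will be summarized by frequency counts for each treatment". The second depends on the result: "If photosensitization occurs, the 95% confidence interval for the proportion of subjects with photosensitization for each product will be calculated". The section does not say how the interval is to be computed or whether it is two-sided. It also says that statistical methods will not decide whether a reaction is photosensitivity; the Investigator does that.

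Section 4.2 justifies the sample size by convention: "The sample size of 50 evaluable subjects conforms to industry and regulatory standards for determination of irritation/sensitization". It gives no assumed rate, power or precision.

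**The concern.** The interval in Section 4.6.2 is the only measure of uncertainty planned for the outcome named in the objective, and it is dropped when nobody reacts. An observed 0% does not show how large a rate 50 subjects can exclude; the upper confidence limit does. Followed as written, the plan would report one reaction in 50 with an interval and none in 50 as a bare zero, which a reader may take as stronger evidence of absence than it is.

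The trigger is also not clearly tied to a product. Suppose one subject reacts to CCP-020 and none to vehicle. One reading gives both products an interval; another gives one to CCP-020 only. Under the first reading, a zero on vehicle is reported with a bound or without one depending on the result for the other product. If both counts are zero, neither product gets an interval under any reading.

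**Working it through.** **Is a bound supplied elsewhere?** Sections 4.1 and 4.6.1 plan an analysis of variance of Induction scores, and Section 4.6.1 adds frequency counts. Section 4.2 has no precision statement. Section 4.7 lists no further topics, and Section 4.9 marks special methods as not applicable. None provides an interval for a zero count.

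**Inputs.** n = 50 evaluable (Sections 3.3.1 and 4.2), confidence level 95% (Section 4.6.2), and zero events as the scenario. The two-sided exact method is assumed because none is named. The plan states no limit or rate, so it has no figure to reproduce.

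**Zero of 50, exact two-sided (Clopper-Pearson).** The upper limit is the rate p at which (1 − p)^n = 0.025, so p = 1 − 0.025^(1/n).
- n = 50: 1 − 0.025^(1/50) = 7.11%. Check: (1 − 0.0711)^50 = 0.025.

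**Dependence on the number evaluable (same formula).**

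| n | upper limit at zero events |
|---|---|
| 45 | 7.87% |
| 50 | 7.11% |
| 55 | 6.49% |
| 60 | 5.96% |

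**Dependence on the method, at 0/50.**

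| method | upper limit |
|---|---|
| exact, two-sided 95% | 7.11% |
| Wilson, z²/(n + z²) = 3.84/53.84 | 7.13% |
| exact, one-sided 95%, 1 − 0.05^(1/50) | 5.82% |
| rule of three, 3/50 | 6.0% |
| Jeffreys, 97.5% point of Beta(0.5, 50.5) | 4.88% |
| Agresti-Coull | 8.52% |
| Wald, 0 ± 1.96·√(0·1/50) | 0% (degenerate) |

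**Comparison: one of 50.** The exact interval runs from the 2.5% point of Beta(1, 50) to the 97.5% point of Beta(2, 49), which is 0.05% to 10.65%. The plan would report this one.

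**How likely is a zero count?** The documents give no expected rate, so the true rates below are assumptions. P(0 of 50) = (1 − p)^50.

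| assumed true rate | P(0 of 50) |
|---|---|
| 0.5% | 77.8% |
| 1% | 60.5% |
| 2% | 36.4% |
| 3% | 21.8% |
| 5% | 7.7% |

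The chance is one half at p = 1 − 0.5^(1/50) = 1.38%. Zero reactions is therefore the more likely result only if the true rate is below about 1.4%, but it remains quite possible at 2% or 3%.

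**The case against.** The strongest reply is that little turns on this. The Investigator makes the diagnosis, no threshold uses the interval, and anyone given the count and the denominator can compute the limit. Nothing in the protocol forbids adding it at reporting, and Section 3.4.5.2 refers to a statistical analysis plan still to be finalized. No separate plan is among the documents, so whether it adds a bound cannot be checked.

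Most of this is true and limits the point to one of reporting. It does not remove it. A reader could equally compute the interval for one reaction, yet the protocol specifies that one in advance, so it already treats precision as relevant to the incidence.

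Three narrower points stand:
- The 7.1% depends on the method, which the protocol leaves open. Removing the condition without naming a method would still allow a Wald interval of 0% to 0% at a zero count.
- The denominator is subjects who complete Challenge. Section 3.3.3 allows discontinuation after an early Induction reaction and requires it once the site has been moved twice for severe tape-related irritation. The limit therefore describes completers, not everyone exposed.
- The per-product ambiguity matters only under one reading. The case of zero on both products carries the point without it.

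**Conclusion.** The concern holds. As written, Section 4.6.2 attaches no uncertainty to a finding of no reactions, which is the finding that most needs it given the objective. Under an exact two-sided 95% interval and 50 evaluable subjects, the omitted statement is that a photosensitization rate up to about 7.1% cannot be excluded (5.8% with a one-sided 95% limit). That limit applies to healthy subjects who complete Challenge under this patch and irradiation procedure, and not to clinical use. The diagnosis itself is unaffected and no estimate is biased. The text should still be corrected, because the omission falls only on the favourable result and is simple to remove.

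**What to change.** In Section 4.6.2, replace the conditional sentence with one to this effect: *For each product, an exact (Clopper-Pearson) two-sided 95% confidence interval for the proportion of evaluable subjects photosensitized will be reported whatever the number of reactions, including zero.* This removes the condition, settles the per-product reading and rules out a degenerate interval at zero. Wilson would give nearly the same limit.

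In Section 4.2, add: *With 50 evaluable subjects and no reactions, the upper 95% limit would be about 7.1%; it will be recalculated for the number actually evaluable.* This second edit is not needed to repair Section 4.6.2, but it shows in advance what the sample size can exclude. If a separate statistical analysis plan is issued, it should carry the same wording.

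The cost is two sentences, with no added subjects, visits or data. The one drawback for the sponsor is that a result of no reactions will read slightly less favourably.
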